3.4. ANALYSIS OF SAFETY

3.4.1. CONCOMITANT IMMUNOMODULATORY TREATMENT

The frequency and duration of use of concomitant immunosuppressant medications will be listed for individual participant and summarized by ATC pharmacologic class. “Concomitant” is defined as any intervention with a start date on or after the date of SPK-8016 administration. The combinations of medications will be considered in the reports. The duration of individual or combinations of immunosuppressant medication will exclude the interruptions between the dosing changes.

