SPK-8016 (adeno-associated viral vector with a [REDACTED] [REDACTED]) is being developed by Spark Therapeutics for the treatment of hemophilia A in patients including those with FVIII inhibitors. This initial clinical study (SPK-8016-101) will evaluate the safety, efficacy, and tolerability of SPK-8016 in adult males with clinically severe hemophilia A and no measurable inhibitor against FVIII. The data obtained from this study will inform the design and dose selection for subsequent studies of SPK-8016 in other patient populations (e.g., those with inhibitors).

In this SPK-8016-101 study, 4 participants have already received SPK-8016 at a dose level of 5×10^{11} vg/kg. Reactive corticosteroids have been administered to avoid the loss of factor VIII transgene expression. This reactive treatment was initiated ~ 3-6 weeks after vector administration in response to a change in the alanine aminotransferase (ALT), FVIII, or ELISpot. Three of the participants required prolonged tapering of daily oral corticosteroids (total courses of 43-48 weeks prednisone) to avoid and treat late recurrences of apparent hepatocyte-targeted immune response. For 2 of these participants, it was clinically necessary to initiate a steroid sparing regimen (i.e., [REDACTED]) to aid in the prednisone taper.

Additional investigation will be needed to determine whether there is a short course immunosuppressive regimen that will reliably control immune responses in all patients and allow long-term expression of the donated gene. Going forward, administration of SPK-8016, beginning at the 1×10^{12} vg/kg dose, will be explored in 2 cohorts chosen based on prior clinical studies, non-clinical studies, and input from clinical experts in rheumatology, organ transplantation, viral immunology, and bone marrow transplantation. [REDACTED]

[REDACTED] prior to vector infusion in an effort to prevent the immune response. In the follow up period, corticosteroids will only be administered if triggered by the clinical observation of increased liver transaminases or decreased circulating FVIII. The ELISpot will not be considered a predictive tool independent of other immune triggers. [REDACTED]

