11. Are unable or unwilling to comply with the schedule of visits and study assessments described in the clinical protocol.

Study Duration: The total duration of the study is approximately 68 weeks, including up to 16 weeks for screening. The study will include the following phases:

- a) Screening period (up to a maximum of 16 weeks);
- b) Study Intervention/Dosing day (Day 0);

Follow-up observation period (52 [\pm 2] weeks).

Planned Number of Participants: Up to 40 evaluable participants will be dosed with a single intravenous infusion of SPK-8016.

Number and Location of Study Sites: The study is planned to be conducted at approximately 15 study centers (vector-administration centers and/or follow-up centers) worldwide.

Sequence of Enrollment: Two staggering strategies are employed in this study:

- a) The first 2 participants in each dose level will be infused with SPK-8016 at least 6 weeks apart to mitigate acute safety risk; and
- b) There will be at least 6 weeks of staggering between each dose level. The Data Monitoring Committee (DMC) will review at least 6 weeks of follow-up data from up to 4 participants who have received SPK-8016 at a given dose level prior to infusing the first participant in the next dose level.
- c) Continued enrollment will alternate between Cohort 1 and Cohort 2 beginning at 1×10^{12} vg/kg. A stagger of at least 4 weeks will occur between the first and the second participants in Cohort 2 (See Figure 1).

The dose level for Cohorts 1 & 2 will begin at 1×10^{12} dose to explore immunomodulation. Cohort 1 will utilize [REDACTED] [REDACTED] begun approximately 48 hours prior to and for 13 weeks following vector infusion. Cohort 2 will utilize [REDACTED] administered prior to vector infusion.

HIV positive individuals with stable CD4+ count >200 mm³ are eligible provided all other inclusion criteria are met. However, they will not be enrolled as the first 2 participants in Cohort 2.

Criteria for Evaluation: **Safety Evaluation:** Safety will be assessed by physical examination, vital signs, adverse events, measurement of antibodies against FVIII, immune responses against transgene product and/or vector, vector shedding of bodily fluids,

laboratory parameter changes over time, and the use of any immunosuppressive therapy.

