7.4 Treatment Compliance

Compliance with the infusion of FVIII protein product and SPK-8016 on the morning of Day 0 will be verified and recorded by trained site staff.

Participants will self-infuse with 50 IU/kg of their usual FVIII protein product per the product insert. Supervision from the site staff is permitted. Number of vials, total volume, and total dosage will be monitored and recorded by the site staff.

Cohort 1 will initiate [REDACTED] approximately 48 hours prior to Day 0. The time of administration will be monitored and recorded by the study staff. Participants in Cohort 2 will be infused with [REDACTED] after FVIII administration and will be supervised by the study staff. The relevant information will be monitored and recorded by the site staff.

[REDACTED]

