7.9.1 Concomitant Therapy

Any medication or vaccine (including over-the-counter or prescription medicines, vitamins, and/or herbal supplements) that the participant is receiving 30 days prior to screening, at the time of enrollment or during the study must be recorded in the eCRF along with:

- Reason for use
- Dates of administration including start and end dates
- Dosage information including dose and frequency

Participants taking medication routinely for a pre-existing condition should be on a regimen, which has been stable for at least 3 weeks, and dosage changes should not be anticipated during the post-infusion period for this study. Any dose change during the study must be documented in the participant's record and eCRF. The Investigator or designee should review the list of all current medications, over the counter medications, vitamins, and herbal supplements. Any concomitant medication that has known hepatotoxicity should be discontinued in the first 12 weeks following vector infusion. The Medical Monitor should be contacted if there are any questions regarding concomitant or prior therapy.

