1.2.3. SAFETY ENDPOINTS

For safety and tolerability:

- Exposure of immunomodulatory treatment
- Adverse events (SPK-8016 related and immunomodulation-related)
- Clinical laboratory evaluation

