3.9.4. PRIOR MEDICATION

Prior medications will be summarized by ATC classification and product name preferred term by participant. Prior medications are those which have a start date prior to SPK-8016 infusion date.

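### The SAP's start-date rule for concomitant immunosuppressants leaves out the planned Cohort 1 agent, which begins about 48 hours before vector

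*SAP*

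**What the plan says.** SAP 1.2.3 names "Exposure of immunomodulatory treatment" as a safety endpoint. In the SAP text available, section 3.4.1 is where it is analysed: frequency and duration of immunosuppressant use, listed by participant and summarised by ATC class, with combinations considered. The section covers concomitant drugs only, and concomitant "is defined as any intervention with a start date on or after the date of SPK-8016 administration".

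SAP 3.9.4 takes everything else: "Prior medications are those which have a start date prior to SPK-8016 infusion date". That output is by ATC class and preferred term; no duration or combination is specified.

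The SAP states that it is based on Protocol Amendment 2. In that protocol's summary (Sequence of Enrollment), the Cohort 1 agent is "begun approximately 48 hours prior to and for 13 weeks following vector infusion". Section 7.4 repeats the start: "approximately 48 hours prior to Day 0. The time of administration will be monitored and recorded by the study staff".

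**The concern.** The two SAP definitions split drugs by start date alone. Neither provides for a drug begun before infusion and still being taken at infusion, yet that is how the Cohort 1 regimen is designed. Almost the whole course is given after vector, but its start date makes it prior medication.

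Reactive corticosteroids are not the problem. In the follow-up period, "corticosteroids will only be administered if triggered by the clinical observation of increased liver transaminases or decreased circulating FVIII", so they start after vector and are captured. Two things are lost for a Cohort 1 participant:

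- the planned agent's own post-vector duration;
- its overlap with corticosteroids, so that combined use could be reported as corticosteroid alone.

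There is also a mismatch with SAP 3.4.2, which analyses adverse events related to immunomodulation agents whatever the drug's start date. Events from Day 0 attributed to the planned agent would be counted there, while the 3.4.1 exposure output could show no exposure to it. Cohorts 1 and 2 were added to explore immunomodulation, so this exposure is of direct interest.

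**Working it through.** The SAP gives no figure to reproduce. The check applies the 3.4.1 rule to the protocol's Cohort 1 schedule.

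**Inputs**

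- Start: about 48 hours before vector, taken as Day -2 (Protocol Summary; Protocol 7.4).
- Stop: 13 weeks after vector, 13 × 7 = Day 91 (Protocol Summary).
- Rule: a record counts only if its start day is 0 or later (SAP 3.4.1).
- Day count: stop − start + 1. SAP 3.7.3 states this formula for adverse events and procedures; using it for drugs is an assumption.

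**Planned course**

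- Total: 91 − (−2) + 1 = 94 days.
- Before vector: Day -2 and Day -1, 2 days.
- On or after Day 0: 91 − 0 + 1 = 92 days (91 without the +1).

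**Counted under the rule**

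With one record, the start is Day -2, so 0 of 92 days count. If a dose change opens a second record on Day k, that record counts for 91 − k + 1 = 92 − k days, and k of the 92 are lost. The values of k are assumed because the regimen text is redacted.

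| Records | Days counted | Post-vector days lost |
|---|---|---|
| New record on Day 7 | 85 | 7 of 92 (7.6%) |
| New record on Day 28 | 64 | 28 of 92 (30.4%) |
| New record on Day 56 | 36 | 56 of 92 (60.9%) |
| One record | 0 | 92 of 92 (100%) |

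**Combinations, as illustration only**

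The documents do not allow the overlap with corticosteroids to be estimated. Suppose a reactive course began at week 3 or week 6, the range reported for earlier participants in Protocol 4.1.3, and lasted at least to Day 91. The overlap would be 91 − 21 + 1 = 71 days or 91 − 42 + 1 = 50 days. With one record for the planned agent, none of it would be reported as combined use.

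**Who is affected**

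The protocol says that "4 participants have already received SPK-8016 at a dose level of" 5×10^11 vg/kg. Cohorts 1 and 2 begin at 1×10^12 vg/kg (Protocol 4.1.1), so those four are outside the problem.

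**The case against.** The strongest objection is that no affected participant is shown. The only dosing in the documents is at the level below the one where Cohort 1 begins. The SAP supports an aCSR, describes development in the past tense and never mentions Cohort 1. This stands as a limit on the practical effect. It does not show that Cohort 1 was empty: the SAP cites Amendment 2 and does not restrict itself to those four participants.

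Second, complete loss requires a single record. Protocol 7.9.1 asks for dose changes to be documented in the eCRF, and SAP 3.4.1 and 3.7.3 speak of gaps between dosing changes, which suggests that several records per drug are possible. Partial loss may therefore be the more realistic case, and the redacted regimen prevents an estimate. But a safety endpoint should not depend on how a course was split at data entry.

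Third, the agent would still be visible under prior medications. That is correct, but its duration and combinations are not restored there. The appendix of tables and listings (SAP 4) is not available, so a separate listing of planned immunomodulators cannot be ruled out.

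Finally, the analysis is descriptive, and exposure duration is not a primary or secondary endpoint in the protocol. That limits the consequence. The SAP nevertheless makes it a safety endpoint and should define it correctly.

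**Conclusion.** The concern holds: SAP 3.4.1 is wrong as written for Cohort 1. For any participant dosed there, between k and all 92 of the post-vector days of planned immunomodulation drop out of the exposure duration, where k is the day of the first new record after infusion. The loss is 100% with one record, and about 8% to 61% in the split-record scenarios shown.

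This rests on the protocol schedule being followed (Day -2 to Day 91), on the day-count formula borrowed from SAP 3.7.3, and on assumed dates of dose change. The effect is nil for the four participants shown as dosed, and nil overall if nobody was dosed in Cohort 1. The wording gap itself is certain, and the correction should be made.

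**What to change.** In SAP 3.4.1:

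- Define concomitant immunosuppressants as those started on or after SPK-8016 infusion, or started before it and ongoing at it, plus any protocol-mandated pre-vector immunomodulator dose. The last part also covers a Cohort 2 infusion given on the calendar day before vector, which the 4-to-24-hour window in Protocol 4.1.6 permits and the present rule would exclude.
- Report pre-vector and post-vector days separately.
- Use all of these drugs when deriving combinations.
- State the duration formula for medications, since SAP 3.7.3 gives one only for adverse events and procedures.

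The cost is a clause of text and a change to the derivation. No new data are needed: Protocol 7.9.1 already requires "Dates of administration including start and end dates" in the eCRF. Results for the four participants shown as dosed do not change, and no clinical rule is touched.

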3.4.2. ADVERSE EVENTS

A treatment-emergent adverse event (TEAE) is defined as an adverse event (AE) with an onset date on or following SPK-8016 administration. The number, frequency and severity of AEs, TEAEs and serious treatment-emergent adverse events (TESAEs) will be categorized and analyzed by all events, events related to SPK-8016 or Immunomodulation agents. All summaries will be classified by Common Terminology Criteria for Adverse Events (CTCAE) version 5.0, by MedDRA version 24.0 system organ class (SOC) and preferred term. TEAEs will be also classified by maximum severity.

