9.1 Definitions

9.1.1 Adverse Event

An AE is any untoward medical occurrence in a patient or clinical investigation participant administered a pharmaceutical product and which does not necessarily have a causal relationship with this treatment. An AE can therefore be any unfavorable and unintended sign (including an abnormal laboratory finding), symptom, or disease temporally associated with the use of a medicinal (investigational) product, whether or not related to the medicinal (investigational) product.

All AEs must be documented regardless of causality.

Events meeting the AE definition include:

- Any abnormal laboratory test results (hematology, clinical chemistry, or urinalysis) or other safety assessments (e.g., ECG, radiological scans, vital signs measurements), including those that worsen from baseline, considered clinically significant in the medical and scientific judgment of the Investigator (i.e., not related to progression of underlying disease).
- Exacerbation of a chronic or intermittent pre-existing condition including either an increase in frequency and/or intensity of the condition.
- New conditions detected or diagnosed after investigational product administration even though it may have been present at one time before the start of the study.
- Signs, symptoms, or the clinical sequelae of a suspected drug-drug interaction.
- Signs, symptoms, or the clinical sequelae of a suspected overdose of either investigational product or a concomitant medication. Overdose per se will not be reported as an AE/SAE unless it is an intentional overdose taken with possible suicidal/self-harming intent. Such overdoses should be reported regardless of sequelae.

Lack of perceived efficacy, failure of expected pharmacological action, or similar assessment will not necessarily be reported as an AE. Such instances will be captured in the efficacy assessments. However, if signs, symptoms and/or clinical sequelae resulting from lack of efficacy meet the definition of an SAE, they will be reported as such.

Events that do NOT meet the AE definition include:

- In this population, bleeding episodes are not considered AEs. All bleeding episodes will be captured in the eCRF. If serious criteria apply (see Section 9.1.2), the event should be reported as an SAE.

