9.4 Follow-up and Reporting Requirements

9.4.1 Follow-up of AEs and SAEs

After the initial AE/SAE report, the Investigator is required to proactively follow each participant at subsequent visits/contacts. All AE/SAEs will be followed until resolution, stabilization, the event is otherwise explained, or the participant is lost to follow-up.

New or updated information will be recorded in the originally completed eCRF and SAE form.

The Investigator will submit any updated SAE data to the Sponsor within 24 hours of receipt of the information.

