9.5 Time Period and Frequency for Collecting AE and/or SAE Information

9.5.1 Time Period and Frequency for Collecting of AEs and SAEs

All AEs and SAEs will be recorded during the period from the signing of the informed consent form (ICF) until the EOS visit at the time points specified in the Schedule of Events.

Medical occurrences that begin before signing of the informed consent form will be recorded in the Medical History section of the eCRF not in the AE section.

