10.5 Primary and Secondary Endpoints

10.5.1 Safety Analysis

For the analysis of safety, the incidence and severity of AEs will be tabulated. Changes from baseline in clinical laboratory variables (including FVIII inhibitor and laboratory parameters for thrombotic potential), vital signs, and physical examination findings will be summarized by descriptive statistics.

All adverse events will be tabulated by occurrence, grouped by body system, and summarized by dose group. The rate of occurrence for each adverse event will be summarized by body system, severity, and relation to the administration of SPK-8016. All SAEs will be summarized separately.

Physical examination and clinical laboratory value abnormalities will be summarized by time point. Values and changes from baseline of key safety parameters (e.g., LFTs) at each time point will be tabulated. Exploratory analysis of safety parameters may be done by tabulating transitions from baseline to the EOS visit at Week 52 (e.g., normal to normal, normal to abnormal, etc.).

Descriptive statistics will be used to evaluate the occurrence of hepatic transaminase elevation requiring immunosuppression and the incidence of immune responses to AAV capsid protein and [REDACTED].

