LDH	Lactate dehydrogenase
mITT	Modified Intention to Treat
PBMC	Peripheral blood mononuclear cells
PK	Pharmacokinetics
RBC	Red blood cell
SAE	Serious treatment-emergent adverse event
SD	Standard deviation
SOC	System organ class

SPK-8016	Study drug in this protocol  
TEAE	Treatment-emergent adverse event
WBC	White blood cell

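### The SAP defines a TEAE by onset date alone, so an AE already open at infusion that worsens or turns serious after SPK-8016 can miss the TEAE and TESAE summaries

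*SAP*

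**What the plan says.** The treatment-emergence rule is in SAP 3.4.2: "A treatment-emergent adverse event (TEAE) is defined as an adverse event (AE) with an onset date on or following SPK-8016 administration". Neither document gives another. The same section sets out what is summarised: "The number, frequency and severity of AEs, TEAEs and serious treatment-emergent adverse events (TESAEs) will be categorized and analyzed by all events", with further breakdowns by relatedness to SPK-8016 or to immunomodulation. TEAEs are also classified by maximum severity. The SAP abbreviation list expands SAE itself as "Serious treatment-emergent adverse event".

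The Protocol governs how the records arise:

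- Section 9.5.1 sets the collection period: "All AEs and SAEs will be recorded during the period from the signing of the informed consent form (ICF) until the EOS visit". Earlier problems go elsewhere: "Medical occurrences that begin before signing of the informed consent form will be recorded in the Medical History section of the eCRF".
- Section 9.4.1, on follow-up after the initial report, says: "New or updated information will be recorded in the originally completed eCRF and SAE form".
- Section 9.1.1 lists among events that are AEs: "Exacerbation of a chronic or intermittent pre-existing condition including either an increase in frequency and/or intensity of the condition". It also lists clinically significant laboratory or other safety findings, including those worse than at baseline.
- Section 10.5.1 says of serious events: "All SAEs will be summarized separately".

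**The concern.** Treatment emergence is meant to separate what appears or gets worse after treatment from what was there before. A test on onset date alone captures only the first part. A mild AE that starts in screening, is still open at infusion, and becomes severe or serious after gene transfer is a post-treatment change, yet the rule places it with the pre-treatment events.

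Safety and tolerability are a primary objective. The TEAE and TESAE tables are where a reader will look for what happened after the vector, and the dose groups are very small. Serious events matter most. The Protocol promises a summary of all SAEs, while the SAP text offers only the treatment-emergent ones.

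**Working it through.** The plan has no figure to reproduce, and no hypothesis is tested. The check applies the rule to a sequence of events and compares the sections.

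**1. Can a pre-vector AE record exist?** Yes. Collection starts at consent (Protocol 9.5.1), and screening may last up to 16 weeks (Protocol 4.2.1). That is 16 × 7 = 112 days at most. Against total participation of up to 68 weeks, 16/68 = 23.5%. This is the longest possible share of time before the vector, not an estimate of how many events are affected.

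**2. Which onset date does the record carry?** SAP 3.7.2 computes days to onset as the event date minus the infusion date. Under SAP 3.4.2 an AE is a TEAE if this value is 0 or more. The days below are assumed for illustration.

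| Course | How the site records the change | Days to onset | TEAE? | TESAE if serious? | In all-AE summary? |
|---|---|---|---|---|---|
| Onset Day −10, worse or serious Day +5 | Updates the existing record | −10 | No | No | Yes |
| Onset Day −1 (Cohort 1, after immunomodulation begins about 48 hours before the vector), worse Day +3 | Updates the existing record | −1 | No | No | Yes |
| Onset Day −10, worse or serious Day +5 | Opens a new record dated Day +5 | +5 | Yes | Yes | Yes |

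**3. Which row do the documents call for?** For an AE already reported, the recording instruction is Protocol 9.4.1, which points to the existing eCRF and SAE form (rows 1 and 2). Protocol 9.1.1 makes an exacerbation of a pre-existing condition an AE. That fits a condition held in medical history, for which no AE record is yet open. Neither document requires a new record when an AE first reported after consent gets worse, so row 3 is possible but not required. Two sites could count the same clinical course differently.

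**4. Where would a serious event in row 1 be summarised?** Protocol 10.5.1 covers it, because its commitment is to all SAEs. SAP 3.4.2 names AEs, TEAEs and TESAEs, and the abbreviation list restricts SAE to treatment-emergent events. No serious-event summary named in the SAP text would contain it.

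**5. Direction and size.** Adding a worsening clause can only bring events into the TEAE and TESAE sets, so its absence can only lower those counts and the TEAE maximum severity. Protocol 4.1.3 reports 4 participants dosed at 5×10¹¹ vg/kg. In a group of that size one event is 1/4 = 25 percentage points, for example a TESAE incidence of 1/4 shown as 0/4. The documents do not give the number of AEs that were open at infusion and later worsened.

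**The case against.** The strongest reply is that the event is not lost. The primary safety endpoint in Protocol 3.3 is the incidence of AEs, not of TEAEs, and SAP 3.4.2 summarises all AEs by number, frequency, severity and relatedness. This stands. A reader might infer that the primary AE-incidence endpoint is understated or that the event disappears from the report. The documents do not support either. What is lost is its place in the TEAE and TESAE summaries and any sign that it worsened after the vector.

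Second, Protocol 9.4.1 says where new information is written. It does not forbid a new record or say in terms that the onset date is kept, and eCRF completion rules are not among the documents. Section 9.1.1 gives a partial route to a separate AE through its exacerbation and laboratory-worsening items. This also stands, so the point is conditional on the site updating the existing record. It would be too strong to say that every such event is misclassified.

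Third, a reader might infer that the TEAE rule as a whole can only bias counts downward. It cannot be put that way. The rule works on dates, so an AE on Day 0 but before the vector, for example after that morning's FVIII infusion, counts as a TEAE and pushes counts up. The downward direction belongs only to the missing worsening clause.

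Fourth, the tables and listings are set out in an SAP appendix that is not in the available text and might include an all-SAE display. That is possible, but the SAP's own definitions point the other way.

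Finally, eligibility is rechecked before dosing, and the stopping rules, AESI monitoring and 24-hour SAE reporting do not use the TEAE flag. These checks reduce the pool of ongoing events and protect safety oversight. They do not exclude a mild ongoing AE that later worsens, and they do not correct the summaries.

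**Conclusion.** The point holds in conditional form. When a site updates the existing record, an AE that began between consent and SPK-8016 and then worsened or became serious is absent from the TEAE counts, the TEAE maximum-severity classification and the TESAE summary. It stays in the all-AE summaries without being identified as post-vector worsening. The SAP text also falls short of the Protocol's commitment on SAEs.

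The frequency is unknown and may be zero. The 25-point figure is the effect of one event in a 4-man group, not a forecast. The conclusion assumes that no eCRF instruction outside these documents requires a new record on worsening, and that the SAP appendix adds no all-SAE summary. Safety oversight during the trial is not affected. The amendment is worth making because a stated rule misplaces a kind of event that the safety report should show, and the correction is cheap.

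**What to change.** In SAP 3.4.2, keep the existing date rule and add: *or an AE with onset before SPK-8016 administration that increases in severity or becomes serious on or after the date of SPK-8016 administration*. Wording the addition by date leaves the handling of Day 0 events unchanged; a reference to the start of infusion would turn the date rule into a clock-time rule.

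State how the change is dated: either the recorded date of the severity or seriousness change, or a new AE record for the worsening with its own onset date.

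Summarise all SAEs, flagging which are treatment-emergent, to match Protocol 10.5.1, and correct the SAE entry in the abbreviation list.

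The cost is one or two SAP sentences, a re-derived flag and a query on AEs that were ongoing at infusion. TEAE and TESAE counts may rise slightly. If no such event occurred, the TEAE and TESAE counts do not change and the report can say so.
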